**Title: Healthcare Utilization in Obese Caregiver Living Donors**

**NCT04341896**

**Date: December 16, 2024**

**Study Protocol and Statistical Analysis Plan (with Results)**

## PROTOCOL

**Study population.** 25,352 donors from 278 centers will be studied. Contact information for donors was provided by the Scientific Registry of Transplant Recipients (SRTR) and is verified using Lexis Nexis Accurint. We anticipate that approximately 20% (n=5,070) of this cohort will have served as the primary caregiver for their recipient. Characteristics of the overall cohort and the subset of caregiver donors are in Table 1. Moreover, the subset of caregivers > 50 years is greater than the whole cohort, further highlighting the need for aging research in this population.

Table 1. Characteristics of obese living donors

	1R01DK113980 (Overall cohort) (n=25,232)	Subset of caregiver donors (n=5,070)
Age in years, median (IQR)	41 (33-49)	46 (39-53)
Age 50+ years, %	23.8	38.6
Female, %	58.4	65.0
Minority race/ethnicity, %	18.5	17.0

**Donor questionnaire.** All participants are contacted through a centralized phone bank maintained by the parent R01's PI at UAB and are administered a survey by phone, mail, or email. The following data are collected and maintained using a robust, redundant, secure, web-based computer entry system (REDCap): demographics (gender, date of birth, race/ethnicity); socioeconomic (education, employment, marital status); family history of comorbid disease; follow-up (frequency of doctor visits pre and post-donation); comorbidities pre and post-donation (smoking, cardiovascular disease, diabetes, etc.), current hypertension, diabetes, or chronic kidney disease/end-stage renal disease, and mental health quality of life. Patients are contacted for follow-up surveys annually. Furthermore, we will leverage the infrastructure of the parent R01 to collect new primary data specific to caregivers. Among those who were the primary caregivers for their recipients, we will administer additional questions derived from the Bakas Caregiver Outcomes Scale and National Alliance for Caregiving quantitative interviews, to describe their physical and mental health at time of donation, including self-reported caregiver burden and benefit pre and post-donation, the economic impact of caregiving, and the caregiving role in the context of donation.

**Medical records abstraction.** During completion of the questionnaire, donors are asked to provide signed waivers for medical records requests from their primary and other care providers. Pre-donation medical records are obtained from the transplant center. Post-donation medical records are obtained from the transplant center, as available, and from the participants' medical providers over time.

**Aim 1: To assess emergency department utilization associated with caregiving among a cohort of living kidney donors who were obese at the time of donation.** We will leverage an existing multi-center R01 study of a national cohort of obese living kidney donors, to quantify the association between a donor reporting that they served as the primary caregiver for the transplant recipient and ED utilization using generalized estimating equations. We will adjust for baseline characteristics and will explore the presence of effect modification and interaction between caregiving status and donor age, race/ethnicity, and rurality.

**Study population.** The study population will consist of living donors with obesity identified by the parent R01, categorized by whether or not they served as the primary caregiver for their transplant recipient. Donors will be stratified by relationship to the recipient (parent, child, spouse/life partner, other caregiver) and sex to allow us to explore sex as a biological variable. We estimate that approximately 20% (n=5,070) were the caregiver for their recipient, of whom 40% were  $\geq 50$  years old (3%  $> 65$  years), and 17% were minorities.

**Definition of caregiver.** Donors are asked whether they served as the primary caregiver (i.e., the main individual who provided unpaid caregiving activities pre and post-donation) for their transplant recipient.

**Definition of outcome of interest.** As part of the parent R01, healthcare utilization data are obtained from the questionnaire and include whether donors have utilized the ED since donation. Donors are asked to report not only whether they used the ED as well as the frequency of use.

**Aim 2: To assess hospitalization associated with caregiving among a cohort of living kidney donors who were obese at the time of donation.** We will use the same cohort from Aim 1 to quantify the association between a donor reporting that they served as the primary caregiver for their transplant recipient and hospitalization using generalized estimating equations.

**Study population.** The same study population identified in Aim 1 will be used.

**Definition of outcome of interest.** The parent R01 also captures data on whether the donor has been hospitalized since donation and the number of times the donor has been hospitalized.

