## RESULTS

Among 784 donors (median 10.4yrs post-donation), 148 (18.9%) identified as caregivers. Caregiver donors were older (62.6 vs. 57.9yrs,  $p < 0.001$ ), more often female (69.6% vs. 58.3%,  $p=0.01$ ), the recipient's spouse (50.0% vs. 7.9%) or parent (16.2% vs. 4.6%,  $p < 0.001$ ), and retired (38.4% vs. 24.9%,  $p=0.004$ ), with no racial differences. Among those identifying as the caregiver and responding to the question about hospitalization ( $n=138$ ), 71 (51.5%) reported having been admitted to the hospital since donation, compared to 237 (40.3%) among non-caregivers. Among those identifying as the caregiver and responding to the question about emergency room utilization since donation ( $n=144$ ), 77 (53.5%) reported having been admitted to the hospital since donation, compared to 305 (49.4%) among non-caregivers.

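### The plan names about 25,000 donors, but 784 (3.1%) are analysed with no account of the rest and no comparison with the cohort, and selection is only partly addressed

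*Combined protocol and SAP*

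**What the plan says.** PROTOCOL, Study population: "25,352 donors from 278 centers will be studied". The overall column of Table 1 is headed 25,232. On caregivers: "We anticipate that approximately 20% (n=5,070) of this cohort will have served as the primary caregiver for their recipient".

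PROTOCOL, Donor questionnaire: "All participants are contacted through a centralized phone bank", with the survey given by phone, mail or email and repeated each year. Contact details are verified. Aim 1 describes the source as national: "We will leverage an existing multi-center R01 study of a national cohort of obese living kidney donors". Caregiver status comes from the survey itself: "Donors are asked whether they served as the primary caregiver".

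STATISTICAL DESIGN AND POWER plans GEE for any use, Poisson regression for counts among users, and interactions of caregiving with age, race/ethnicity and rurality. Baseline adjustment is stated for Aim 1. The Aim 2 text carries over the interaction work but does not repeat the adjustment. Neither aim gives an expected response rate, a comparison of analysed donors with the cohort, weighting, or a sensitivity analysis for selection.

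RESULTS: "Among 784 donors (median 10.4yrs post-donation), 148 (18.9%) identified as caregivers". For hospitalization, "71 (51.5%) reported having been admitted to the hospital since donation, compared to 237 (40.3%) among non-caregivers". Item denominators are given for caregivers only (138 for hospitalization, 144 for ED).

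**The concern.** About 97% of the named cohort is missing from the results without explanation. The donors concerned may not have been contacted, reached or surveyed yet, or may have declined. A reader therefore cannot judge how far the 784 resemble the donors the plan set out to study.

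Two things are at stake. First, the reported proportions describe the national cohort only if the 784 resemble it in age, time since donation and health. Second, the caregiver odds ratio (OR) could be affected in two ways:

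- If the association varies with age, an average over an older sample is not the cohort average.
- If inclusion depends on utilization and caregiver status jointly, the OR itself is distorted. Separate multiplicative effects of each on inclusion would leave it unchanged. Covariate adjustment does not repair the joint case.

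**Working it through.** **Plan's own figures.** 0.20 × 25,352 = 5,070.4, so 5,070 comes from the text total; 0.20 × 25,232 = 5,046. In RESULTS, 148/784 = 18.9%, as printed.

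**Share analysed.** 784/25,352 = 3.09% and 784/25,232 = 3.11%, so 3.1% either way. Caregivers: 148/5,070 = 2.9%. Donors not accounted for: 25,352 − 784 = 24,568.

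**Where the loss occurs.** Non-caregivers: 784 − 148 = 636. Their item denominators follow from the printed percentages: 237/0.403 gives 588, and 305/0.494 gives 617 or 618 (both round to 49.4%). RESULTS words the ED finding as hospital admission; it is read here as ED use.

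| Item not answered | Caregivers | Non-caregivers |
|---|---|---|
| Hospitalization | 10/148 = 6.8% | 48/636 = 7.5% |
| ED | 4/148 = 2.7% | 18 or 19/636 = 2.8-3.0% |

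Item non-response is small and similar by group. Nearly all the loss comes before the outcome questions.

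**Comparison with Table 1.** This assumes that RESULTS ages are at survey and Table 1 ages at donation; neither is stated.

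- All donors: (148 × 62.6 + 636 × 57.9)/784 = 58.8; 58.8 − 10.4 = 48.4, against 41. Gap 7.4 years.
- Caregivers: 62.6 − 10.4 = 52.2, against 46. Gap 6.2 years.
- Female: (148 × 0.696 + 636 × 0.583)/784 = 60.4%, against 58.4%.
- Race/ethnicity: RESULTS gives no percentages.

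The age figures are crude. Means and medians may be mixed, one overall follow-up median is subtracted from both groups, and the source of the caregiver column is not stated. If both sets of ages refer to the same time point, the overall gap is 58.8 − 41 = 17.8 years.

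**Illustration for a proportion.** Pooled hospitalization is (71 + 237)/(138 + 588) = 308/726 = 42.4%, with 95% half-width 1.96 × √(0.424 × 0.576/726) = 3.6 points. The documents give no age gradient, so one is assumed. Take a logistic model in age with SD (49 − 33)/1.349 = 11.86, fix the intercept to give 42.4% at mean 48.4, and average over mean 41:

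| Assumed OR per 10 years | Proportion at cohort ages | Change (points) |
|---|---|---|
| 1.0 | 42.4% | 0 |
| 1.2 | 39.2% | 3.2 |
| 1.5 | 35.7% | 6.8 |

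Only the steepest gradient moves the figure by more than its half-width. Age alone is standardised. Time since donation also matters, because the outcomes accumulate after donation, but the cohort's follow-up is not given.

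**Illustration for the OR.** If the caregiver OR changes by a factor of 1.1 to 1.25 per 10 years of age (assumed), a 7.4-year shift moves it by 1.1^0.74 = 1.07 to 1.25^0.74 = 1.18, that is 7-18%. Sampling error is larger. The crude hospitalization OR is (71 × 351)/(67 × 237) = 1.57 (95% CI 1.08-2.28), a factor of about 1.45 either way. The crude ED OR, with 617, is (77 × 312)/(67 × 305) = 1.18 (0.82-1.69).

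**Cost of weighting (age only, normal approximation).** Design effect = exp((shift/SD)²): exp((6.2/11.86)²) = 1.31 and exp((7.4/11.86)²) = 1.48. Square roots are 1.15 and 1.21, so intervals are 15-21% wider. Effective n is about 597 to 531 of 784.

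**The case against.** Both aims concern an association; national prevalence is not an aim. RESULTS conditions its hospitalization figure on answering the item ("Among those identifying as the caregiver and responding to the question about hospitalization") and makes no national claim. Adjustment covers selection on the adjusted covariates, and the planned caregiver-by-age analysis would show directly whether the OR varies with age. Weighting on age, sex and race/ethnicity largely repeats that adjustment, cannot include caregiver status or utilization, and costs precision. The age illustrations rest on assumed gradients and ages of unstated time point, and the OR shift lies well inside sampling error. The caregiver share (18.9% vs 20%) and sex are close to the cohort's.

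Much of this stands. It rules out three stronger readings that a reader might infer:

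- *That no planned step touches selection.* The adjustment and the interaction do so in part.
- *That 3.1% is a response rate.* It is a fraction analysed; the number contacted is not given.
- *That the caregiver association is biased.* Nothing in the documents shows this.

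It does not answer the reporting gap. Verified contact details, three survey modes and annual re-contact may raise response, but they neither measure nor correct selection. A caregiver share near plan says nothing about outcomes. Selection on unmeasured factors, or jointly on utilization and caregiver status, is not addressed.

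**Conclusion.** The point holds as a gap in reporting and analysis that should be closed; no bias is demonstrated. The size named in the plan was not delivered: 784 of about 25,000 donors, and 148 of about 5,070 caregivers, with no account of the rest and no comparison with the cohort. These facts depend on no assumption, and the choice between 25,352 and 25,232 does not change the 3.1%.

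That the sample is older (about 48 vs 41 at donation) is suggested only, under the stated assumption about when ages were taken. The 0 to 6.8 point and 7-18% figures are illustrations and do not carry the conclusion. Size and direction of any selection effect cannot be determined from the documents. It would be wrong to read the reported proportions as known to be off for the national cohort; they are simply not shown to apply to it.

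**What to change.** 1. **Size, flow and comparison.** Restate the analysed size as 784 donors, 148 of them caregivers, with item denominators of 138 vs about 588 for hospitalization and 144 vs 617-618 for ED (exact counts from the data). Reconcile 25,352 with 25,232. As far as the parent study's records allow, report numbers contacted, reached, responding and answering the caregiver item, then numbers answering each outcome item by caregiver group. Tabulate the 784 against the full cohort on the Table 1 variables, with age at donation and the same summary measure in both columns.
2. **Conclusions.** Limit them to the analysed donors, and do not present the proportions as national-cohort figures.
3. **Analysis.** Keep the planned GEE and Poisson models as the main analysis, with baseline adjustment stated for both aims. Add one sensitivity analysis, labelled as added after results. Model inclusion among all cohort donors on baseline variables held for everyone, including donation year or time since donation if available. Weight the proportions and caregiver ORs by inverse probability of inclusion, use robust standard errors clustered on donor, and report the effective n.

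The cost is analysis time and retrieval of whatever contact records the parent study holds, with no new donor contact. The weighted intervals will be wider, by roughly 15-21% under the age-only approximation and possibly more with further variables. Caregiver status cannot enter the weights because it is unknown in donors not surveyed. The report should say that weighting cannot correct selection that depends on utilization and caregiver status.

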## STATISTICAL DESIGN AND POWER

**Aim 1. Power calculation.** Goren et al. demonstrated a significant difference in ED utilization by caregiver status (7.2% for caregivers vs. 4.0% for non-caregivers). Assuming a two-tailed test and a proportion of 4% experiencing ED use in the non-caregiver group, we will have 99% power to detect a relative risk of 1.8 for ED utilization among caregivers vs. non-caregivers. This is likely an underestimate, given that individuals with obesity have a greater use of hospital services, and incidence is likely to be higher in our cohort.

**Aim 1. Statistical analyses.** We will explore post-donation ED use by caregiver status, using generalized estimating equations (GEE) accounting for repeated measurements, to estimate whether odds of ED use differ by caregiver status. We will use Poisson regression to explore count of ED visits among those who report having used these services by caregiver status, adjusting for baseline characteristics, including demographic, socioeconomic, and health status at donation. We will explore the presence of effect modification and interaction between caregiving status and donor age, race/ethnicity, and rurality. As a sub-aim, we will explore whether utilization differs by self-reported physical, mental, and financial burden among caregiver donors.

**Aim 2. Power calculation.** Goren et al. demonstrated a significant difference in the proportion of Alzheimer's caregivers experiencing hospitalization (8.1% for caregivers vs. 5.1% for non-caregivers). Assuming a two-tailed test and a proportion of 5% experiencing hospitalization in the non-caregiver group, we will have 99% power to detect a relative risk of 1.6 for hospitalization among caregivers vs. non-caregivers. This is likely an underestimate, given that this study was performed in Japan, and hospital admissions for many preventable diseases are higher in the United States than in other countries.

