**Aim 2. Statistical analyses.** We will explore odds of post-donation hospitalization by caregiver status, first using generalized estimating equations to account for repeated measurements, then using Poisson regression to explore the counts of hospitalization among those who report having used these services. As in Aim 1, we will explore the presence of effect modification and interaction by stratification and interaction terms between caregiving status and donor age, ethnicity, and rurality, in addition to exploring the role of self-reported burden in hospitalization among the subset of caregiver donors.

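### Both binary outcomes accumulate from donation, but no planned model names time since donation; if it differs by caregiver status, the caregiver odds ratios are biased

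*Combined protocol and SAP*

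**What the plan says.** **Outcomes.** In the PROTOCOL, the Aim 1 outcome definition states that "healthcare utilization data are obtained from the questionnaire and include whether donors have utilized the ED since donation". The Aim 2 definition captures "whether the donor has been hospitalized since donation and the number of times the donor has been hospitalized". The ED count is described only as follows: "Donors are asked to report not only whether they used the ED as well as the frequency of use". No start point is given for that count.

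**Surveys.** Under Donor questionnaire: "Patients are contacted for follow-up surveys annually". Whether a follow-up survey asks about the whole period from donation or only about the time since the last survey is not stated.

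**Models.** Under STATISTICAL DESIGN AND POWER, Aim 1 is analysed "using generalized estimating equations (GEE) accounting for repeated measurements, to estimate whether odds of ED use differ by caregiver status". The Aim 1 summary in the PROTOCOL adds "We will adjust for baseline characteristics". The examples come in the sentence on the Poisson count model: "adjusting for baseline characteristics, including demographic, socioeconomic, and health status at donation". Aim 2 follows the same pattern, GEE first, "then using Poisson regression to explore the counts of hospitalization among those who report having used these services". Its analysis text names effect modifiers but no adjustment covariates.

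**Time at risk.** No section names years since donation, donation year or an exposure offset as a model term. Follow-up appears once, in RESULTS, as a median of 10.4 years for all 784 donors, with no spread and no split by caregiver status.

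**The concern.** A question about any event since donation has a different length of exposure for each donor. A donor surveyed at 14 years has had twice as long to visit an ED as one surveyed at 7. Two groups with the same event rate but different follow-up will therefore show different proportions, and the odds ratio will differ from 1 without any effect of caregiving.

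Neither planned feature deals with this. GEE handles correlation between reports from the same donor, not unequal time at risk. Adjustment for characteristics at donation does not carry elapsed time either, because elapsed time is not a baseline characteristic.

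At stake is the interpretation of the main estimate in both aims. The unstated survey window adds an ambiguity of its own. The repeated-measures odds could describe ever-use status at each wave or new use in each interval, and these are different quantities needing different time terms.

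**Working it through.** The plan gives no figure for time at risk by group, so a corrected odds ratio cannot be computed. The stated 99% power contains no follow-up time and does not bear on this point. The check is therefore a sensitivity calculation.

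**Inputs from RESULTS.**
- Hospitalization: caregivers 71/138; non-caregivers 237 (40.3%), implying 237/0.403 ≈ 588.
- ED use: caregivers 77/144; non-caregivers 305 (49.4%), implying 305/0.494 ≈ 617. The sentence giving these figures concerns the emergency room question but is worded as hospital admission; they are taken here as ED use.
- Median follow-up, pooled: 10.4 years.

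**Crude odds ratios** (Wald 95% CI).
- Hospitalization: (71 × 351)/(67 × 237) = 1.57 (1.08 to 2.28).
- ED use: (77 × 312)/(67 × 305) = 1.18 (0.82 to 1.69).

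**Assumptions.** There is no true caregiver effect, and all non-caregivers are at 10.4 years. The probability of no event by time t is S(t) = exp(−ht), or (1 + vht)^(−1/v) with gamma frailty of variance v. For each v, h is refitted so that 1 − S(10.4) equals the non-caregiver proportion.

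**Worked case, v = 0.**
- ED: h = −ln(1 − 0.4943)/10.4 = 0.0656. At 11.4 years the proportion is 1 − exp(−0.0656 × 11.4) = 0.526. The null odds ratio is (0.526/0.474)/(0.494/0.506) = 1.14.
- Hospitalization: h = −ln(1 − 0.4031)/10.4 = 0.0496. At 11.4 years the proportion is 0.432 and the null odds ratio is 1.13.

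**Null odds ratio from follow-up alone**, v = 0 / 0.5 / 1 / 2:

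| Caregiver follow-up | ED use | Hospitalization |
|---|---|---|
| 3 years shorter | 0.64 / 0.68 / 0.71 / 0.77 | 0.66 / 0.69 / 0.71 / 0.76 |
| 1 year shorter | 0.87 / 0.89 / 0.90 / 0.93 | 0.88 / 0.89 / 0.90 / 0.92 |
| 1 year longer | 1.14 / 1.11 / 1.10 / 1.07 | 1.13 / 1.11 / 1.10 / 1.08 |
| 3 years longer | 1.44 / 1.35 / 1.29 / 1.21 | 1.40 / 1.34 / 1.29 / 1.22 |

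**These are not bounds.** In an ageing cohort the hazard may rise. Take a Weibull shape of 1.5 with no frailty. The cumulative hazard at 13.4 years is its value at 10.4 years times (13.4/10.4)^1.5 = 1.46. The proportions become 0.631 (ED) and 0.530 (hospitalization), and the null odds ratios 1.75 and 1.67.

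**Counts among users, if they also run from donation.** The mean count among users is ht/(1 − S(t)). For ED with v = 0 it is 0.682/0.494 = 1.38 at 10.4 years and 0.747/0.526 = 1.42 at 11.4 years, a ratio of 1.03 with no true effect. Dividing by the time ratio 11.4/10.4 = 1.096, as a plain log-time offset does, gives 0.94. Over both outcomes and v from 0 to 2, one extra year gives 1.02 to 1.06 without an offset and 0.93 to 0.97 with one. A plain offset among users does not remove the bias; it reverses the direction.

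**The case against.** **The harm is conditional.** Nothing in the documents shows that follow-up differs by caregiver status. RESULTS gives crude proportions and no fitted odds ratio, the analyses are described as exploratory, and the covariate list is open-ended, so silence does not prove that time will be left out. All of this stands, and it is why the point is put conditionally. It does not remove the gap: a longer list of baseline characteristics would still not contain elapsed time, and a reader cannot check the balance from a pooled median.

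**A reader might infer that follow-up explains the observed hospitalization difference.** The documents do not support that. Under the assumptions above, the whole gap would need 4.2 to 8.3 extra caregiver years with constant hazard and frailty variance 0 to 2, or 2.6 with the Weibull shape of 1.5. No follow-up by group is given to set against these figures. The crude odds ratio is also not the planned adjusted estimate.

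**A reader might turn to the ages for evidence of balance or imbalance.** They are uninformative. Table 1 sets caregivers (median 46) against the overall cohort that contains them (41), whereas RESULTS sets caregivers (62.6) against non-caregivers (57.9). Treating medians as means with 20% caregivers, the non-caregiver age in Table 1 would be (41 − 0.2 × 46)/0.8 = 39.75, a gap of 6.25 years against 4.7 in RESULTS. But RESULTS does not say when age was measured. If it was at survey, subtracting 10.4 gives 52.2 and 47.5 at donation, well above Table 1, so the 784 donors do not resemble the full cohort.

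**The count models.** No window is stated for the ED count, and that for hospitalizations is only implied, so that part of the point is conditional. The choice of count model is partly preference.

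**Conclusion.** The point holds in conditional form and should be fixed. Both binary outcomes accumulate from donation, and the plan as written leaves unequal time at risk uncorrected. If time since donation differs by caregiver status, the odds ratios are biased upward when caregivers have been followed longer and downward when they have been followed for less time. Which of these applies, if either, cannot be told from the documents, and the bias may be nil.

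For scale only, an imbalance of one year moves a null odds ratio by roughly 7% to 14%. Three extra years move it to between 1.21 and 1.44, or about 1.7 under a rising hazard. These figures rest on no true effect, all non-caregivers at 10.4 years, inferred non-caregiver denominators and the assumed hazard shapes.

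It would go too far to say that the reported contrasts are biased, or that adding a time term would rule bias out. The time term must be correctly specified and matched to the survey window, and it does nothing about selective response.

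**What to change.** 1. **Establish the window first.** State, for each survey and each question (any use and count), whether it covers the period from donation or only the time since the last survey. This is a sentence in the SAP; the questionnaire belongs to the parent study and completed surveys cannot be reworded.
2. **Put the matching time term in the GEE models for both aims.** Where the window runs from donation, add years since donation at the survey, flexibly (for example a 3-df spline), and interpret the result as ever-use status at each wave. Where it runs from the last survey, use the interval length for those reports.
3. **Report median (IQR) years since donation by caregiver status.** This is one table row and lets a reader judge whether the bias matters.
4. **Counts, only if they also run from donation.** Account for time at risk with a method suited to users only, for example a zero-truncated model with a log-time offset. This keeps the planned users-only question at the price of a more complex model.

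The pooled 10.4-year median implies that time since donation is already held, so items 2 and 3 need SAP wording and a re-run. Three degrees of freedom are few against 77 + 305 = 382 donors reporting ED use and 71 + 237 = 308 reporting hospitalization. The change reduces bias from unequal follow-up; it does not correct for who responded.

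### The only stated look-back for ED use and hospitalization is cumulative from donation, yet both aims fit GEE to annual repeated measurements, so the odds ratio would mix ever-use with length of follow-up

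*Combined protocol and SAP*

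**What the plan says.** - **Outcomes.** Under Aim 1, Definition of outcome of interest, "healthcare utilization data are obtained from the questionnaire and include whether donors have utilized the ED since donation"; frequency of use is also asked. Under the same heading in Aim 2, the parent study records "whether the donor has been hospitalized since donation and the number of times the donor has been hospitalized".
- **Surveys.** Under Donor questionnaire: "Patients are contacted for follow-up surveys annually". The wording of the follow-up items is not given.
- **Analysis.** Aim 1 compares ED use by caregiver status "using generalized estimating equations (GEE) accounting for repeated measurements, to estimate whether odds of ED use differ by caregiver status". Aim 2 does so for hospitalization, "first using generalized estimating equations to account for repeated measurements". For counts: "We will use Poisson regression to explore count of ED visits among those who report having used these services by caregiver status". The covariates named are baseline characteristics at donation. Time since donation is not among them, and no offset is stated.
- **Exposure.** Under Definition of caregiver, one past-tense yes/no item covers caregiving before and after donation, without dates or duration.
- **Follow-up reached.** Results: "Among 784 donors (median 10.4yrs post-donation), 148 (18.9%) identified as caregivers". One cumulative proportion per group is given for each outcome, with no repeated-measures estimate.

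**The concern.** A cumulative yes/no outcome and a repeated-measures model do not fit together. Once a donor reports any use, each later answer to the same question must also be yes. Further surveys then add little information, and donors with more surveys can contribute the same old event several times. The fitted odds are the odds of having ever used the service by the survey date, which rise with elapsed time even when the underlying rate is constant. If caregivers and non-caregivers differ in time since donation, that difference enters the odds ratio.

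The caregiver item carries no dates. The contrast therefore cannot separate a short-lived excess around donation from a lasting one, and the two move the planned odds ratio in opposite directions relative to its one-year value. A small or null estimate could not be read as no effect during caregiving, and a large one could not be read as a large annual effect.

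**Working it through.** **Inputs.** From Results: median T = 10.4 years since donation; non-caregivers with ED use 49.4%, with hospitalization 40.3%. The ED sentence there ends by speaking of hospital admission; it is read here as ED use because it opens on emergency room use. From the power sections: relative risks 1.8 (ED) and 1.6 (hospitalization), non-caregiver proportions 4% and 5%. Assumed: constant rates, every donor at the median follow-up, two-sided alpha 0.05, and D years of raised risk.

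**1. The plan's own figure.** A two-proportion test with 5,070 caregivers and 25,352 − 5,070 = 20,282 non-caregivers has power above 99.99% for 7.2% vs 4% and for 8% vs 5%, so the stated 99% is met. Those proportions are not on the cumulative scale: 1.8 × 49.4% = 88.9% of caregivers would need ED use for the planned relative risk to hold there.

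**2. Carry-over.** Rate r = −ln(1 − P)/T.
- ED: −ln(0.506)/10.4 = 0.0655 per year. At 11.4 years, 1 − exp(−0.0655 × 11.4) = 52.6%. Share already yes a year before: 49.4/52.6 = 94%.
- Hospitalization: −ln(0.597)/10.4 = 0.0496 per year. At 11.4 years, 43.2%. Share already yes: 40.3/43.2 = 93%.

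Only 52.6 − 49.4 = 3.2 percentage points of ED answers change in the year, although 1 − exp(−0.0655) = 6.3% of donors would have some ED use in it.

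**3. Length of follow-up.** Take two groups with the same ED rate, observed for 10.4 and 12.4 years. Ever-use is 49.4% and 1 − exp(−0.0655 × 12.4) = 55.6%. The odds ratio is (0.556/0.444)/(0.494/0.506) = 1.28 with no difference in rate.

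**4. Duration of the effect.** Caregiver ever-use is P1 = 1 − exp(−r × [T + (RR − 1) × D]). For ED and D = 2: 1 − exp(−0.0655 × 12.0) = 54.4%, so the ratio is 54.4/49.4 = 1.10 and the odds ratio (0.544/0.456)/(0.494/0.506) = 1.22.

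| Years of raised risk | ED, 1.8-fold rate: P1 | RR | OR | Hospitalization, 1.6-fold rate: P1 | RR | OR |
|---|---|---|---|---|---|---|
| 1 | 52.0% | 1.05 | 1.11 | 42.1% | 1.04 | 1.08 |
| 2 | 54.4% | 1.10 | 1.22 | 43.7% | 1.09 | 1.15 |
| 5 | 61.1% | 1.24 | 1.61 | 48.6% | 1.20 | 1.40 |
| 10.4 | 70.7% | 1.43 | 2.47 | 56.2% | 1.39 | 1.90 |

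For comparison, one year at the raised rate gives OR 1.85 for ED (11.1% vs 6.3%) and 1.62 for hospitalization (7.6% vs 4.8%).

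**5. Observed crude contrasts.** Back-calculated non-caregiver denominators are 305/0.494 ≈ 617 and 237/0.403 ≈ 588. ED: 77/144 vs 305/617, RR 1.08 (95% CI 0.91 to 1.28), OR 1.18. Hospitalization: 71/138 vs 237/588, RR 1.28 (1.06 to 1.54), OR 1.57.

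**The case against.** Several stronger readings are tempting, and the documents do not support them.

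- **That every annual survey asks about use since donation.** The follow-up items are not shown and could cover only the interval. This stands, so the carry-over is conditional on the outcome being repeated as defined. But no other definition is given, and the Results report the cumulative one.
- **That visit counts are re-entered at each wave.** The text ties repeated measurements to the GEE for odds. It does not say that the Poisson model pools surveys.
- **That any effect of caregiving is diluted.** Attenuation needs an effect confined to part of follow-up. With a lasting effect the planned measure, an odds ratio, grows. No duration is given, caregiving is defined as spanning donation, and half of the caregivers in the Results are spouses of the recipient.
- **That a real difference is washed out.** The crude hospitalization RR of 1.28 shows that the cumulative measure can register one. It is unadjusted, and caregivers were older (62.6 vs 57.9 years), so it does not establish a caregiving effect.

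Two further defences have weight. Ever-caregiver against use since donation is a coherent observational contrast and matches the aim as worded, so it should be kept, but once per donor. Robust GEE variance also deals with within-donor correlation, so standard errors are not the main issue. It does not change what the odds ratio describes. Finally, the added caregiver questions cover burden and benefit before and after donation. Their items are not shown, so timing questions cannot be ruled out.

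**Conclusion.** The point holds as a gap in specification with a definite consequence. Followed as written, the repeated outcome cannot revert, about 93 to 94% of yes answers one year on repeat earlier ones, and the odds ratio reflects ever-use mixed with follow-up time rather than new use.

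The effect on the estimate has no fixed direction. For a 1.8-fold ED rate lasting 1 to 5 years, the RR is 1.05 to 1.24 and the OR 1.11 to 1.61; lasting all 10.4 years, they are 1.43 and 2.47. Unequal time since donation can move the odds ratio either way.

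These sizes rest on constant rates, an assumed duration of raised risk, and the 10.4-year median among the 784 donors in the Results, which is not a planned follow-up length. The plan should be changed, but the documents do not show that its results are biased towards no effect.

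**What to change.** 1. **First survey.** Keep the since-donation question and analyse it once per donor, with time since donation in the model: for example, a complementary log-log model for ever-use and a count model, each with a log-time offset. Under the constant-rate model, the former estimates the rate ratio averaged over follow-up: (10.4 + 0.8 × D)/10.4, which is 1.08, 1.15, 1.38 and 1.80 for D = 1, 2, 5 and 10.4. This removes the mixing with follow-up length and the growth of the odds ratio. It does not recover a short-lived effect.
2. **Annual follow-ups.** Ask about ED use and hospitalization since the last survey, and make that the repeated outcome in the GEE. If the follow-up items already ask this, state it in the SAP.
3. **Surveys already done.** Take differences between consecutive reported counts, and check for and report negative values.
4. **Caregiving timing.** Add the caregiving end date to the caregiver questions, for a secondary analysis by timing. Current caregiving status should not define the main analysis: so long after donation few donors may still be exposed, and the period around donation would be lost.

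**Cost.** A changed recall window, an added item in a questionnaire already being extended for caregivers, and SAP text. The interval analysis uses only donors with at least one follow-up survey, does not cover the period around donation, and has fewer events: about 6.3% with ED use per year against 49.4% cumulatively, or roughly 144 × 0.063 = 9 caregivers a year among those who answered the ED question. Differenced recalled counts are noisy.
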